10.1 Statistical and Analytical Plans

A detailed statistical and analytical plan will be finalized in consultation with the study biostatistician and determined prior to study outcomes analysis. Preliminary approaches are described below but some details of specific statistical analysis plans may change upon biostatistics consultation and/or as the study progresses; no changes in the analysis plan would change the risk to study participants. For minor statistical plan changes, protocol modification approval will not be sought from the IRB.

10.2 Statistical Hypotheses

We hypothesize that ED patients receiving the Relay peer navigator intervention after a nonfatal OD will have significantly fewer opioid-related adverse events (opioid OD and substance use related ED visits) in the next 12 months compared to patients receiving site-directed care.

10.3 Analysis Datasets

The primary dataset will contain all randomized study participants and will include data both from participant assessments (at baseline, 1-, 3-, and 6-months) and from a 12-month administrative data extraction/review. The primary analysis will be intent-to-treat (ITT). Depending on the amount of crossover between study arms other analyses may be conducted upon consultation with the study biostatistician.

Secondary datasets will include the Relay program data as maintained by the DOHMH and a qualitative interview dataset (audio recordings which will be transcribed). Of note, Relay program data forms were developed and are administered by DOHMH. Relay program data forms may be changed by DOHMH without notice, as this is an element of the DOHMH-operated program not under the direct control of the researchers. Such modifications will not be submitted for IRB approval.

CONFIDENTIAL

This material is the property of the NYU School of Medicine and NYU Langone Health. Do not disclose or use except as authorized in writing by the study sponsor
Behavioral Intervention Template Version: 11 January 2019

10.4 Description of Statistical Methods

10.4.1 General Approach

Two-arm RCT comparing site-directed care (SDC) to the Relay intervention among patients presenting to the ED with a nonfatal opioid-involved OD.

10.4.2 Analysis of the Primary Efficacy Endpoint(s)

The primary endpoint is the number of opioid-related adverse events in the 12 months following the index ED visit. Opioid-related adverse events include: any opioid-involved OD (fatal or nonfatal) or any other substance use-related ED visit. Overdose deaths are tracked using the DOHMH comprehensive database of NYC overdose deaths. Data on OD resulting in ED visits or other substance use related ED visits will be collected from administrative data at 12 months, as identified from visit chief complaint and/or diagnoses. We will collect additional self-reported data on OD using a questionnaire that has been used in prior studies. This questionnaire will be administered at each study visit. Participants will be asked whether the OD did or did not result in an ED visit. We will use this information to calculate an estimated 12 month opioid-related OD event count.

The primary outcome will be ascertained by administrative data abstraction with adjustment using self-report data as described above. Administrative data extraction will be completed by members of the study team who are blinded to participant arm assignment. Results for the primary outcome will be compared for independent data abstraction completed by two members of the study team; disagreements will be resolved either by consensus or by a study PI.

The primary analysis will use a Poisson generalized linear regression model to evaluate the intervention effect on the total number of opioid-related adverse events. We anticipate the availability of 12 months of follow-up data on all participants but, in the event of death or withdrawal from the study, we will adjust the follow-up time appropriately using an offset term. We will include adjustment for study site, as well as other baseline factors that may be unbalanced across arms. The primary effect measure will be the incidence rate ratio comparing Relay to SDC. Some participants may be routinely high utilizers of the ED, and this may lead to overdispersion of the count outcome; we will therefore use a negative binomial model instead of a Poisson model if warranted.

In summary, the primary outcome is “opioid-related adverse events,” which will include fatal and non-fatal opioid-involved overdose as well as substance use-related emergency department (ED) visits. ED visits and fatal overdoses in the 12-month period after baseline will be captured in administrative data sources. Other non-fatal opioid-involved overdose events will be captured by self-report in follow-up interviews through six months after baseline, and estimated for the second half of the 12-month follow-up period.

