8.7 Study Halting Rules

Decisions about halting or terminating the study will be made by the PIs in conjunction with the DSMB. The study will be halted if:

- There are significant deficiencies in study performance and/or quality control such that continuation of the study would be dangerous, unethical, or would not be expected to result in meaningful results despite modification.
- There are significant risks to participant safety as indicated by frequency of reportable serious adverse events or protocol violations that put participants at risk.
- The study stopping rule is met. The stopping rule will be based on the objective, serious, negative event of fatal opioid overdose. The study will be stopped if we observe a rate ratio of number of OD deaths in the SDC arm to number of OD deaths in the Relay arm of ≥ 3.0 and a one-sided p-value of <0.01 , or a one-side p-value of $<.01$ when the rate ratio is undefined due to zero deaths in the Relay arm. The DOHMH will provide the study investigators with data on any OD deaths for study participants biannually. The DSMB will review all overdose deaths of study participants at each biannual DSMB meeting. The DSMB will use the overdose death data to determine whether the stopping rule has been met at each biannual DSMB meeting after at least 80 total participants have been enrolled in the study, at which point differences between the study arms can be determined with reasonable statistical precision.

In the event that the study is halted, researchers will attempt to contact participants to inform them and potentially offer additional services.

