10.6 Measures to Minimize Bias

10.6.1 Enrollment/Randomization/Masking Procedures

At the enrollment visit, the RA will use an electronic system (REDCap) to trigger assignment to a treatment arm. Randomization will use a 1:1 ratio and is stratified by site; permuted blocks with variable blocks of size 4 and 6 will be used to maintain balance over time and prevent prediction of assignment by the RA. Upon randomization, the RA will immediately inform the participant of the treatment arm assigned.

While the RA conducting the baseline assessment cannot be blinded to the intervention assignment (since it will occur during the same ED visit as the intervention), whenever possible a different RA will be assigned to conduct follow-up interviews in an attempt to maintain blinding. Blinding may be imperfect since participants may reveal their intervention assignment, including based on their answers to the follow-up assessments. Participants themselves cannot be blinded to the treatment condition due to the nature of the intervention. Study staff conducting the administrative data abstraction for the primary study outcomes will be blinded to the intervention assignment. Study analytic staff are blinded to treatment condition until the conclusion of the trial and finalization of the analytic database.

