10.6.3 Breaking the Study Blind/Participant Code

Not applicable. For any reportable events, the participant's study arm will be noted.

11 Source Documents and Access to Source Data/Documents

Source data is all information, original records of clinical findings, observations, or other activities in a clinical trial necessary for the reconstruction and evaluation of the trial. Source data are contained in

CONFIDENTIAL

This material is the property of the NYU School of Medicine and NYU Langone Health. Do not disclose or use except as authorized in writing by the study sponsor

Behavioral Intervention Template Version: 11 January 2019

source documents. Examples of these original documents, and data records include: hospital records, clinical and office charts, laboratory notes, memoranda, subjects' diaries or evaluation checklists, pharmacy dispensing records, recorded data from automated instruments, copies or transcriptions certified after verification as being accurate and complete, microfiches, photographic negatives, microfilm or magnetic media, x-rays, subject files, and records kept at the pharmacy, at the laboratories, and at medico-technical departments involved in the clinical trial.

For this study documents aside from the study-specific documents as described in this protocol are minimal. Study baseline and follow-up assessments and other participant information collected at baseline will be collected and maintained using REDCap. REDCap maintains a log of any changes to this information. Consent forms will also be collected on REDCap. Relay programmatic data is maintained by DOHMH on a separate system per their existing protocols.

Access to study records will be limited to the study team, including DOHMH study team members as governed by an executed DUA. The investigator will permit study-related monitoring, audits, and inspections by the IRB/EC, the sponsor, government regulatory bodies, and University compliance and quality assurance groups of all study related documents (e.g. source documents, regulatory documents, data collection instruments, study data etc.). The investigator will ensure the capability for inspections of applicable study-related facilities (e.g. pharmacy, diagnostic laboratory, etc.).

Participation as an investigator in this study implies acceptance of potential inspection by government regulatory authorities and applicable University compliance and quality assurance offices.

12 Quality Assurance and Quality Control

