Multiple steps will be taken toward quality assurance (QA) and quality control (QC).

- All study staff will be thoroughly trained both in overall GCP and human subjects protections and in study-specific procedures.
 - Formal training will occur prior to the study beginning recruitment.
 - RAs will be supervised until they are able to conduct study procedures independently.
 - Continuous training will occur in weekly staff team meetings.
- RAs will be closely supervised by the PM, with PI oversight.
- MOP and SOP documents will clearly outline all study procedures, including QA/QC procedures.
- Multiple QA/QC protections are built into REDCap data collection software being used for this study, including forced question entry (i.e., specified questions cannot be left blank), automatic logging of all activities in REDCap including any entry changes, and study staff permission rules.
- Weekly QA/QC reviews conducted by the PM and reviewed/discussed with the PI will include:
 - Review of numbers of patients approached, eligible/ineligible, refused, participated.
 - Review to ensure that all eligibility classifications were made correctly.
 - Review for missing or out of range data.
 - Review for completeness of forms and data.
 - Review of exit surveys for adherence to study protocols.
 - Review of any safety issues.
 - Review of any potential QA/QC issues identified by any study staff member (which did not warrant more immediate discussion).

QC procedures will be implemented beginning with the data entry system and data QC checks that will be run on the database will be generated. Any missing data or data anomalies will be communicated to the site(s) and/or individual RA(s) for clarification/resolution.

CONFIDENTIAL

This material is the property of the NYU School of Medicine and NYU Langone Health. Do not disclose or use except as authorized in writing by the study sponsor
Behavioral Intervention Template Version: 11 January 2019

13 Ethics/Protection of Human Subjects

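### Section 10.4.2 lets a study PI settle disputed primary-outcome events, and nothing in the plan masks the PI, who has access to arm information, in that role

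*Combined protocol and SAP*

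**What the plan says.** Section 10.4.2 sets out blinded, duplicate abstraction of the primary outcome: "Administrative data extraction will be completed by members of the study team who are blinded to participant arm assignment". Two team members work independently and their results are compared. Where they differ, "disagreements will be resolved either by consensus or by a study PI". No order is given between the two routes. Nothing is said about whether the PI is masked or what the PI is shown.

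Section 10.6.1 repeats the protection for abstractors: "Study staff conducting the administrative data abstraction for the primary study outcomes will be blinded to the intervention assignment". It adds one for analysts: "Study analytic staff are blinded to treatment condition until the conclusion of the trial and finalization of the analytic database". Neither sentence names the PI.

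The exit survey is described in Sections 6.1.2 and 10.4.5. Among other things it confirms, by ticked boxes, that SDC participants received the minimum package: overdose education and naloxone, a treatment list and a Relay handout. Section 12 has the Project Manager carry out weekly QA/QC reviews, which are then discussed with the PI. One listed item is "Review of exit surveys for adherence to study protocols". Section 14.1 places downloaded REDCap files on a drive open to the PI, with no mention of masking the arm. Randomization is also run in REDCap (Sections 7.3.1 and 10.6.1).

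**The concern.** Participants know their arm, and Section 10.6.1 accepts that blinding of the follow-up interviewers may fail. Blinded abstraction is therefore the main safeguard for the administrative part of the primary outcome. Whether an ED visit counts as substance use-related is read from the chief complaint and/or diagnoses, which can call for judgement. Visits on which two careful abstractors differ are the ones where judgement matters most and where knowledge of the arm could tip the decision. A tie-break by someone with access to the arm leaves the last step of an otherwise blinded process unprotected. Section 4.2.2 draws the secondary counts of ED visits for opioid OD and for other substance use from administrative data as well, so the same rulings could carry over to them.

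**Working it through.** **Step 1. Who is masked, and who sees the arm.**

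| Role | Masking stated | Route to arm information |
|---|---|---|
| Abstractors | Yes (10.4.2, 10.6.1) | None described |
| Analytic staff | Yes, until the database is final (10.6.1) | None described |
| PI as tie-breaker | Not stated | Exit-survey QA (6.1.2, 10.4.5, 12); downloaded REDCap files (14.1) |

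The exit-survey route is the broadest, because every participant completes the survey. Adherence to a minimum package that applies to one arm cannot be judged without knowing the arm.

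**Step 2. Inputs for the size.** From Section 10.5: 350 participants, 2.0 events per year under SDC, overdispersion 1.6, two-sided 0.05. With 1:1 allocation this is 175 per arm, or 175 × 2.0 = 350 expected events per arm.

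As a check on how the plan uses the 1.6, its power figure was reproduced with the Signorini formula for Poisson regression, multiplying the variance by 1.6 and using b = ln(2.0/1.52) = 0.2744:

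- √(350 × 2.0 × 0.2744² / 1.6) = 5.740
- (5.740 − 2 × 1.96) / √(2 + 2 × 0.76) = 1.820 / 1.876 = 0.970
- Φ(0.970) = 83.4%, against 83% stated. The same formula for 1.75 versus 1.32 gives 80.3%, against 80% stated.

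The match requires the ratio to be applied upward from the SDC rate; a two-sided Wald calculation on the same rates gives 76.0%. That does not bear on this point. It is enough here that 1.6 acts as a variance multiplier.

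**Step 3. Bias under no true effect.** The documents give neither the share of visits reaching the PI nor any difference in rulings by arm, so both are assumed: share 5-15%, difference 10-40 percentage points, with fewer events accepted in the Relay arm.

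- SE(log IRR) = √(1.6 × 2 / 350) = 0.0956
- Apparent IRR = 1 − share × difference
- z = −ln(IRR) / SE
- Type I error = Φ(−1.96 + z) + Φ(−1.96 − z)

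| Share | Difference | IRR | z | Type I error |
|---|---|---|---|---|
| 5% | 10 points | 0.995 | 0.052 | 0.0282 + 0.0221 = 5.0% |
| 10% | 20 points | 0.980 | 0.211 | 0.0402 + 0.0150 = 5.5% |
| 15% | 40 points | 0.940 | 0.647 | 0.0946 + 0.0046 = 9.9% |

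**Step 4. A second parameterisation.** Let a share d of candidate events be disputed and accepted with probability a in each arm. The fraction of candidate events counted in an arm is then 1 − d + d × a, and the SE uses the reduced counts.

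- d = 5%, acceptance 45% (Relay) versus 55% (SDC): IRR 0.9725/0.9775 = 0.995, type I error 5.0%.
- d = 10%, 40% versus 60%: IRR 0.94/0.96 = 0.979, 5.5%.
- d = 20%, 40% versus 60%: IRR 0.88/0.92 = 0.957, 7.3%.
- d = 20%, 25% versus 75%: IRR 0.85/0.95 = 0.895, 19.7%. This is an extreme case, outside the 5-15% and 10-40 point range.

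**The case against.** The strongest reply is that the text is silent on masking of the PI; it does not say the PI is unblinded when ruling. Consensus is the other route, so few visits may reach the PI. Exit surveys are reviewed weekly, around enrolment, while abstraction takes place at 12 months, so the PI would have to recall or look up the arm of one participant among 350. Section 4.2.2 lists ICD codes among the sources for the parallel ED-visit endpoints, which should limit ambiguity. The abstraction tool (Attachment P) is listed but was not available to us, so its decision rules cannot be judged. Self-reported overdoses that did not lead to an ED visit, and deaths from the health department database, enter the outcome without this tie-break, which lowers the disputed share further.

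All of that stands as a limit on the size. It does not close the gap: the rule as written allows the PI to rule on the hardest cases, access to the arm is documented, and no sentence prevents its use.

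A reader might also infer that the PIs see deaths by arm. Section 8.7 says "Decisions about halting or terminating the study will be made by the PIs in conjunction with the DSMB" under a rule comparing the arms, and "The DOHMH will provide the study investigators with data on any OD deaths for study participants biannually". It does not say those data arrive split by arm, and it is the DSMB that determines whether the rule is met. Knowing the arms of participants who died would in any case say little about the arm of another participant with a disputed visit.

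A reader might likewise point to reportable events, for which the "study arm will be noted" (Section 10.6.3). Section 8.4 largely limits these to unanticipated and related events, other unanticipated problems, complaints and major deviations. Section 8.1.1 excludes overdose from AE reporting. Few arms would be revealed this way, so neither route is relied on here.

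**Conclusion.** The point holds in a limited form. The plan does not ensure blinded classification of the disputed ED visits that reach a PI. It would go too far to say that the blinded abstraction is undone, or that the PI is certain to know the arm when ruling: agreed and consensus-resolved events remain protected, and the documents show access rather than use.

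The size is unknown. Under the assumed 5-15% of visits and 10-40 point difference in rulings, the null IRR lies between 0.995 and 0.94 and type I error between 5.0% and 9.9%. The low end is negligible. The high end needs both frequent referral to the PI and rulings that differ strongly by arm. The case for acting rests on the low cost of closing the gap, not on a demonstrated bias.

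**What to change.** In Section 10.4.2, replace the PI route. Disagreements are first resolved by consensus of the two blinded abstractors. Any that remain go to an existing team member who has no access to arm data and who works from the abstracted record with mentions of arm and of Relay removed. Report how many events were decided this way, by arm, once the database is final.

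This is a cheap improvement: a change of wording, a small redaction step, and no added staff. The downside is that the PI gives up the tie-break role. Section 8.7 needs no change for this purpose.

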10.4.3 Analysis of the Secondary Endpoint(s)

Secondary outcome analysis. For secondary outcomes, we will use models similar to those for the primary outcome. Initiation of medication for opioid use disorder (MOUD) in the first 90 days will be evaluated using a logistic regression model with intervention arm as the primary predictor. In addition, we will explore multiple initiations of MOUD in the follow-up period using longitudinal generalized linear mixed models. These will use a logit link and incorporate random effects for participants to accommodate the correlation of repeated assessments. The OD risk behavior score will be evaluated using mixed effects models for continuous longitudinal data, incorporating random effects for participants as described. Item responses to the OD risk behavior questionnaire will be summed; higher scores indicate a higher number and/or frequency of risk behaviors. Time to first subsequent OD will be evaluated using Cox proportional hazards models. Frequency of ED visits for a) opioid OD, b) other substance use related reason, and c) any cause will be evaluated with Poisson regression models as described for the primary outcome. For all models, we will assess validity of assumptions regarding distributional characteristics of the outcomes and find suitable transformations if necessary. We will assess indicators of model fit and evaluate standard model diagnostics such as residual plots.

Qualitative interview analysis. One-on-one interviews will be conducted with approximately 12 patients,
CONFIDENTIAL

This material is the property of the NYU School of Medicine and NYU Langone Health. Do not disclose or use except as authorized in writing by the study sponsor

Behavioral Intervention Template Version: 11 January 2019

10-12 ED providers, and 10 peer navigators, though if we find that important new concepts are emerging in late interviews we will continue interviews until theoretical saturation is reached. Interviews will follow a semi-structured guide with a 'start list' of key questions drawn from the theoretical model and CFIR domains and will allow for exploration of unanticipated themes. Interviews will be digitally recorded and transcribed. Given the immediate pragmatic goals of the analysis (i.e., to identify factors impacting implementation and fidelity) and the desire to quickly translate research findings into practice, the initial analysis of the interviews will use rapid turn-around qualitative methods such as creating templated summaries of interviews and conducting matrix analysis focused on key domains. These techniques are action-focused, time-limited, and facilitate sharing of results, while still being rigorous. A subsequent analysis will include line-by-line coding of all content from the transcripts using an *a priori* coding scheme based on the theoretical model and CFIR domains; researchers will additionally identify any relevant emergent themes. Coding will be done by a core team of 2-3 trained researchers, and findings will be discussed among the investigators to reach consensus on the main themes. ATLAS.ti or Dedoose will be used to assist with coding and data organization.

Relay programmatic data. Additional descriptive analyses will be conducted of Relay programmatic data (e.g., number and types of contacts with participants) to allow a fuller understanding of the Relay intervention.

